### 2.2 Aims and Objectives

#### Aims

1. To establish the metabolic/molecular response in both adipose tissue and skeletal muscle to acute starvation (~82 h).
2. To establish the sensory experience to prolonged fasting (pain, fatigue, drive).

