### *Secondary*

Change in circulating glycerol and FFAs across the prolonged fast (indices of lipolysis from adipose tissue)

Change in Autophagy (in skeletal muscle and neutrophils)

Total nitrogen (or at least urea nitrogen) in urine (24h collection) throughout the fast (or at least 1st vs last day)

Change in plasma lactate and pyruvate in response to prolonged fasting (indices of Cori cycle)

Change in urinary (acetoacetate), and circulating (beta-hydroxybutyrate) ketones in response to prolonged fasting.

Change in body mass, pre-post, and during the prolonged fast.

Change in blood pressure pre-post, and during the prolonged fast.

Change in waist-hip circumferences pre-post the prolonged fast.

Change in sensory experience (pain, fatigue, drive) in response to prolonged fasting.

Change in haematocrit/haemoglobin pre-post the prolonged fast.

Change in grip strength pre-post the prolonged fast.

Change in reaction time pre-post the prolonged fast.

Change in aspects of immune function and infection risk

Change in interstitial fluid glucose concentrations pre-, post-, and during the prolonged fast (assessed via continual glucose monitoring)

Occurrence of adverse events (e.g. nausea, vomiting, migraines)

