### 4. Trial days

3 days prior to the first experimental visit participants will visit the laboratory to be fitted with a continual glucose monitor, an actiheart activity monitor, as well as a food diary and food scales. They will be asked to record energy intake and to standardise physical activity, caffeine, and alcohol intake.

Upon finishing the 3 days of lifestyle standardisation participants will enter the laboratory for where weight, height, waist:hip circumference, sagittal-abdominal diameter, and skin-fold will be assessed prior to assessment of resting metabolic rate, blood pressure and urinary ketones. Participants will also undergo grip strength, reaction time, and sensory experience assessment. Following this, samples of skeletal muscle and adipose tissue will be collected from the *vastus lateralis* and abdominal adipose tissue respectively. An intravenous cannula will then be placed a 10 mL blood samples will be drawn before ingestion of a carbohydrate rich porridge breakfast (7.3 mg carbohydrate·kJ).

A 3-hour postprandial period follows the ingestion of breakfast with blood samples will be collected at 15, 30- and 60-minute intervals during the first, second and third hour respectively alongside hourly expired gas samples and assessment of subjective appetite and mood. Upon completion of the 3-hour post-breakfast period, participants will have completed the visit and will be provided with a standardised lunch and dinner. Participants will also be provided with urinary ketone sticks, a blood pressure monitor, a set of weighing scales, as well as an actiheart monitor.

Participants will be asked to assess urinary ketones using provided assessment sticks in the evening at 2000 h.

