### 5. Intervention

Participants will be provided with their last meal at ~1900 h on the day of the meal testing. From this point onwards, participants will be asked to refrain from eating for ~82 hours until their return visit to the laboratory. Throughout this period of extended fasting participants will be provided with 80 mmol sodium and 40mmol potassium daily (to consume in the form of slow-release tablets) to minimize the confounding effects of fluid deprivation and intravascular volume depletion on cardiovascular reflexes and sympathetic nervous system activity. Subjects will also be permitted to consume water, non-sugared carbonated drinks

and, with the exception of the day of the pre/post measurements, non-sugared decaffeinated coffee and tea (if they normally consume tea and coffee).

Upon waking each day participants will be asked to assess their urinary ketone levels, blood pressure, and weight. Participants will be asked to repeat this in the evening at 2000 h.

Each day participants will be asked to return to the laboratory to provide a blood sample. On the second day of starvation participants will also be asked to provide a blood sample at 2000 h.

Furthermore, throughout the intervention participants will be asked to wear an actiheart monitor in order to assess physical activity levels in response to prolonged fasting.

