## **6. Follow up visit**

Upon completion of the intervention, participants will visit the laboratory at the University of Bath, and repeat the pre-intervention visit with the porridge breakfast. Following this repeated visit, participants will again be provided with a standardised lunch and dinner.

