## **7. Ethical considerations of risk and discomfort**

Acute starvation may cause discomfort for participants including headaches and lack of energy. All participants will be supervised by a member of the research team throughout the protocol. Participants who drop out after one day of fasting will not be included in follow up testing, but will be provided with food to break their fast. Conversely, participants who decide to not continue with study following 2 days of fasting will be asked to come in for follow up testing/standardised meal provision. Biopsies also introduce a risk for discomfort for participants but will only be performed by trained and experienced members of staff who follow the guidelines for safe practice. Intravenous cannulation has the potential to cause minor discomfort and bruising. Furthermore, there is a small associated risk of infection and/or embolism, where blood flow to the vein becomes partially restricted. In order to minimise these risks, cannulation will only be carried out by qualified and experienced staff members. The cannula is an essential aspect will only be in the vein for a maximum of 3 hours per laboratory visit, whereas the venepuncture needle on days 1,2, and 3 of the fast will be removed as soon as the sample is obtained.

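### Any soreness left from the first biopsies, cannula or daily blood draws would be counted as pain from fasting, because only the post-fast pain score follows those procedures

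*Combined protocol and SAP*

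**What the plan says.** All references are to the combined protocol and SAP.

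- **Outcome.** Pain is part of Aim 2 (section 2.2). Section 2.5 lists as a secondary outcome "Change in sensory experience (pain, fatigue, drive) in response to prolonged fasting".
- **Baseline order.** Section 4 puts the score early in the visit: "Participants will also undergo grip strength, reaction time, and sensory experience assessment". The next step is "Following this, samples of skeletal muscle and adipose tissue will be collected from the" vastus lateralis and the abdomen. The cannula, breakfast and 3-hour postprandial period come after that.
- **Start of the fast.** Section 5: "Participants will be provided with their last meal at ~1900 h on the day of the meal testing". Food is then withheld for about 82 h.
- **Follow-up order.** Section 6 has participants "repeat the pre-intervention visit with the porridge breakfast", so the second score again precedes that visit's own biopsies.
- **Between the scores.** Section 5 also asks for a blood sample each day, with an extra evening sample on the second day. Section 7 describes these as venepuncture on fast days 1, 2 and 3.
- **Comparison.** Section 2.4 has one arm, with each participant as their own control. Section 2.6 plans a paired t-test or Wilcoxon test for measures taken only before and after.
- **Discomfort.** Section 7 states that "Biopsies also introduce a risk for discomfort for participants" and that cannulation may cause minor discomfort and bruising. It treats both as ethical matters only.
- **Activity.** A monitor is fitted 3 days before the baseline visit (section 4). During the fast participants "wear an actiheart monitor in order to assess physical activity levels in response to prolonged fasting" (section 5).

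**The concern.** The two pain scores differ in more than feeding state. The first is taken before any biopsy, and the second after two biopsies, a cannula and several blood draws. Everyone is both sampled and fasted, so the two exposures coincide and a paired test cannot tell them apart. If some soreness remains at follow-up, it would be reported as part of the sensory experience of fasting. Keeping the same order at both visits does not balance this, because only the first set of biopsies lies between the scores.

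The documents do not describe the pain instrument, ask for pain by site, or name the biopsies as a limitation when pain is interpreted. If location is not recorded at the time, it cannot be recovered later.

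**Working it through.** **1. Interval from biopsy to second score.** The last meal is at about 1900 h on the biopsy day and the fast lasts about 82 h (section 5). 19 + 82 = 101 h after midnight of that day, which is 4 × 24 + 5, or about 0500 h on the fourth day after it. The documents give no clock time for the biopsies, so I assume 0700 to 1000 h:

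- biopsy at 0700 h: (19 − 7) + 82 = 94 h
- biopsy at 1000 h: (19 − 10) + 82 = 91 h

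The gap is therefore nearly 4 days (91/24 = 3.8; 94/24 = 3.9), longer than the fast itself. The venepunctures on fast days 1 to 3 are closer to the second score.

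**2. What enters the paired change.** Suppose pain is a single overall score to which site soreness simply adds. Then

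observed change = fasting effect + soreness remaining at follow-up.

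The second term is zero or positive, so the bias has one direction. The planned tests have no term that removes it.

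**3. Illustration of size.** The documents contain no pain data, SD or significance level. The planned sample of 6–10 (section 2.6) comes without inputs, so there is no figure of the plan's own to reproduce. Assume a two-sided 5% paired t-test, no fasting effect on pain, and remaining soreness of δ SDs of the paired change. The test rejects with probability

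P(|T| > t₀.₉₇₅,ₙ₋₁), where T is noncentral t with n − 1 degrees of freedom and noncentrality δ√n.

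At n = 6 and δ = 0.5, for example, the noncentrality is 0.5 × √6 = 1.22 and the probability is 0.171.

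| δ (SD of paired change) | n = 6 | n = 8 | n = 10 |
|---|---|---|---|
| 0 | 0.050 | 0.050 | 0.050 |
| 0.25 | 0.080 | 0.094 | 0.109 |
| 0.5 | 0.171 | 0.232 | 0.293 |
| 0.75 | 0.321 | 0.449 | 0.562 |
| 1.0 | 0.507 | 0.681 | 0.803 |

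The same figures would apply to any one-directional disturbance of that size. They show how sensitive the comparison is, and do not estimate how large the soreness will be. The Wilcoxon alternative was not calculated.

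**4. Activity.** The pre-fast record covers the 3 days before the thigh biopsy, and the whole during-fast record follows it. That comparison therefore also spans the biopsy.

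**The case against.** The strongest reply is that nothing shows soreness persisting for nearly 4 days. Section 7 speaks of a risk of discomfort from biopsies and a potential for minor discomfort from cannulation, and gives no duration. This stands. A reader might infer from the order of procedures that the pain outcome is contaminated, or that the larger rejection rates are this trial's false-positive risk. The documents support neither: the order shows only that soreness, if present, would be misattributed.

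The pain instrument might already record location, and the study schematic is not available to check. That is possible, but the text does not say so. If it does record location, the remedy reduces to stating how the ratings will be used.

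The consequence is also limited. Pain is one of three components of one secondary outcome, in a study that describes itself as exploratory. The argument does not reach the meal-response or amino-acid primary outcomes. This stands and limits the weight of the point, although pain is named in one of only two aims.

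On activity, a reader might infer that a fall during the fast would be due to a sore thigh. The documents do not support that either. Activity is not in the section 2.5 outcome list, pre-fast activity is itself to be standardised, and daily laboratory visits also affect the during-fast record. The biopsy is one possible contributor among several.

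**Conclusion.** The point holds in conditional form. Any procedure soreness remaining at the follow-up score would be attributed to fasting under Aim 2, and the plan as written has no means of separating it. The ordering is explicit in sections 4 to 6; the size of the bias is unknown.

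If soreness has resolved, the bias is zero. If 0.25, 0.5 or 1.0 SD of the paired change remains and fasting has no effect on pain, a false effect would be declared in 8–11%, 17–29% or 51–80% of trials at n = 6–10. This assumes a two-sided 5% paired t-test and a single additive pain score. The 91–94 h interval assumes biopsies between 0700 and 1000 h.

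This is a cheap improvement worth making before data collection. The activity comparison is a lesser point that needs only a reporting note.

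**What to change.** - At both sensory assessments, rate pain at procedure sites (biopsy, cannula and venepuncture) separately from pain elsewhere. The venepuncture sites must be included; otherwise their soreness would fall into the second rating.
- State in section 2.5 that the Aim 2 pain outcome is the change in pain excluding procedure sites, and report procedure-site pain alongside it.
- When reporting the Actiheart data, note that the pre-fast versus during-fast comparison spans a thigh biopsy.

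The cost is one extra rating at each sensory assessment and a sentence in section 2.5, with no extra visit, sample or staff. The downsides are a slightly longer form and reliance on participants to locate their pain.

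### The home blood-pressure monitor and scales are issued only after the laboratory baseline, so no pre-fast home reading of weight or blood pressure is scheduled and no same-device baseline is specified

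*Combined protocol and SAP*

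**What the plan says.** The outcome list in section 2.5 includes, as secondary outcomes, the change in body mass and in blood pressure both from before to after the fast and within it; for the latter it reads "Change in blood pressure pre-post, and during the prolonged fast".

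Section 4 (Trial days) sets the order of events:

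- At the fitting visit three days before baseline, participants are "fitted with a continual glucose monitor, an actiheart activity monitor, as well as a food diary and food scales". No blood-pressure monitor or body-weight scales are listed.
- Baseline weight is a laboratory measurement: "participants will enter the laboratory for where weight, height, waist:hip circumference, sagittal-abdominal diameter, and skin-fold will be assessed". Blood pressure is taken at the same visit, once these body measurements are complete. Both come before the porridge breakfast.
- After the 3-hour postprandial period: "Participants will also be provided with urinary ketone sticks, a blood pressure monitor, a set of weighing scales".
- For that evening: "Participants will be asked to assess urinary ketones using provided assessment sticks in the evening at 2000 h". Weight and blood pressure are not mentioned.

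Section 5 (Intervention) starts the fast that same evening: "Participants will be provided with their last meal at ~1900 h on the day of the meal testing". It continues: "Upon waking each day participants will be asked to assess their urinary ketone levels, blood pressure, and weight", with the set repeated at 2000 h. It does not say whether the evening of the meal-test day counts.

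Section 2.6 assigns one-way ANOVA with Bonferroni post-hoc tests to variables assessed each day. It defines no reference level and does not separate morning from evening readings. Section 6 repeats the laboratory visit after the fast.

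**The concern.** A change during the fast needs a starting value measured in the same way. Here the only weight and blood-pressure values clearly scheduled before the fast are taken in the laboratory on one morning, whereas the values during the fast are taken by the participant at home, morning and evening. If the laboratory value is used as the starting point, any systematic home-minus-laboratory difference is added to each during-fast change. That difference may come from setting, from time of day for the evening readings, and from the device if it is not the same one. Analysis cannot remove it afterwards, because no home reading before the fast exists to estimate it. At stake is the within-fast time course of two secondary outcomes.

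**Working it through.** The plan states no figure on this point, so there is none to reproduce. The check has three parts.

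**1. Clock arithmetic.** Inputs: last meal at about 1900 h on the meal-test day (section 5); evening reading at 2000 h (sections 4 and 5); waking at 0700 h (my assumption). With the meal-test day as day 0, hours since the last meal = 24 × day + clock hour − 19.

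| Reading | Day 0 | Day 1 | Day 2 | Day 3 |
|---|---|---|---|---|
| Waking (0700 h) | before devices are issued | 24 + 7 − 19 = 12 | 48 + 7 − 19 = 36 | 72 + 7 − 19 = 60 |
| 2000 h | 20 − 19 = 1 | 24 + 20 − 19 = 25 | 48 + 20 − 19 = 49 | 72 + 20 − 19 = 73 |

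The first home reading of weight and blood pressure that is certain to be scheduled is at about +12 h. The first evening reading of both that is certain is at +25 h. The +1 h evening reading is specified for ketones only. It would be close to a fed-state value if taken, though not strictly before the fast.

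**2. How an offset enters.** Let the true value be T₀ at baseline and T₁ during the fast, and let b be the home-minus-laboratory offset.

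- Laboratory reference: (T₁ + b) − T₀ = true change + b.
- Home reference at the same clock time: (T₁ + b) − (T₀ + b) = true change.

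If b varies between participants with mean β, the mean change is biased by β and the remaining variation adds noise. Only the shared part fails to average out.

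**3. Illustration of size.** Assumptions: no true change; a constant offset of r SDs of the paired change; the laboratory value as reference; two-sided 5% level. The documents give neither an offset nor an SD. The sample sizes 6 and 10 are the ends of the range in section 2.6. The rejection probability is P(|t| > t_crit), where t is noncentral with n − 1 degrees of freedom and noncentrality r√n. For r = 0.5 the noncentrality is 0.5 × √6 = 1.22 and 0.5 × √10 = 1.58. The unadjusted critical values are 2.571 and 2.262.

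| Offset r | n = 6, unadjusted | n = 10, unadjusted | n = 6, Bonferroni over 3 | n = 10, Bonferroni over 3 |
|---|---|---|---|---|
| 0.25 | 8% | 11% | 3% | 4% |
| 0.5 | 17% | 29% | 7% | 15% |
| 1.0 | 51% | 80% | 27% | 60% |

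The nominal rate is 5% in the unadjusted columns and 5%/3 = 1.7% per comparison in the Bonferroni columns (critical values 3.534 and 2.933). With Bonferroni over six comparisons, r = 0.5 gives 4% and 9% against a nominal 5%/6 = 0.8%. On one scale: if the SD of paired weight change were 1.0 kg, r = 0.5 would be an offset of 0.5 kg. Both values are assumed.

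**The case against.** A reader might infer more than the text supports, and several counter-arguments stand.

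- **That the devices differ.** The documents never identify the laboratory scales or monitor, so they do not show that the issued ones are different. What can be said is that no same-device baseline is specified. Setting, and for evening readings time of day, would differ even with identical devices.
- **That the 2000 h readings have no early value at all.** Ketones do have a 2000 h reading on the baseline day. For weight and blood pressure, section 5 can be read as including that evening, since the fast has begun and participants hold the devices. Section 4 names ketones alone. The text is ambiguous rather than plainly silent.
- **That the laboratory baseline is a fed-state value, so every home reading is already deep in the fast.** Baseline weight and blood pressure precede breakfast. The first waking reading, at about +12 h, follows an ordinary overnight interval and can serve as a home reference for later mornings. This stands, although the plan does not designate that reading and it is one value per person.
- **That the percentages describe this trial.** They use a paired t-test, which section 2.6 reserves for variables assessed only before and after the intervention. Daily variables get ANOVA with Bonferroni post-hoc tests, which lowers the per-comparison rates. The figures also need a laboratory reference level that the plan does not state and an offset shared across participants. If each participant's devices err in different directions, part of the error cancels.

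Materiality is also limited. The gap touches the within-fast part of two of the 15 listed secondary outcomes, in a study that section 2.1 describes as exploratory rather than hypothesis driven.

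**Conclusion.** The concern holds in a limited form. Followed as written, the plan has no weight or blood-pressure reading in the home setting that is clearly scheduled before the fast, and it specifies no same-device baseline. The consequence falls on the evening series, which has no assured reference, and on any daily analysis that takes the laboratory value as its starting level. The morning series can be analysed against its first waking value. Laboratory pre-post comparisons of body mass and blood pressure are unaffected, and so are the primary outcomes.

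The size of the bias cannot be derived from the documents. The percentages in the working show only that, at 6 to 10 participants, an offset that is moderate relative to the paired SD would raise false-positive rates well above nominal; they do not predict what will happen. A true change would be shifted by the same offset, up or down. The point merits a change mainly because the remedy is cheap and a pre-fast reading that was never taken cannot be recovered.

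**What to change.** 1. Issue the blood-pressure monitor and scales at the existing fitting visit three days before baseline.
2. Collect waking and 2000 h weight and blood pressure on the control days.
3. State that the 2000 h reading on the meal-test day includes weight and blood pressure as well as ketones, so that sections 4 and 5 agree.
4. In section 2.6, name the reference level for the daily ANOVA as the control-day mean at the same clock time, and analyse morning and evening readings separately.
5. State which devices are used at the laboratory visits.

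Cost: the equipment is out three days longer and participants log a few more readings; no added visit or staff is needed. One drawback remains. Section 4 has participants record their intake on the control days but describes no standardised meals then, so control-day evening weights will carry some meal-related variation. Averaging over the control days reduces this but does not remove it.

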### 5. Intervention

Participants will be provided with their last meal at ~1900 h on the day of the meal testing. From this point onwards, participants will be asked to refrain from eating for ~82 hours until their return visit to the laboratory. Throughout this period of extended fasting participants will be provided with 80 mmol sodium and 40mmol potassium daily (to consume in the form of slow-release tablets) to minimize the confounding effects of fluid deprivation and intravascular volume depletion on cardiovascular reflexes and sympathetic nervous system activity. Subjects will also be permitted to consume water, non-sugared carbonated drinks

and, with the exception of the day of the pre/post measurements, non-sugared decaffeinated coffee and tea (if they normally consume tea and coffee).

Upon waking each day participants will be asked to assess their urinary ketone levels, blood pressure, and weight. Participants will be asked to repeat this in the evening at 2000 h.

Each day participants will be asked to return to the laboratory to provide a blood sample. On the second day of starvation participants will also be asked to provide a blood sample at 2000 h.

Furthermore, throughout the intervention participants will be asked to wear an actiheart monitor in order to assess physical activity levels in response to prolonged fasting.

